3.3.2.2 Diarrhea

Diarrhea should be treated with standard medications to avoid dose modification or interruption, if possible. Diarrhea related to ZD6474 has been successfully managed with anti-diarrheal agents such as loperamide. Once diarrhea is determined to be related to ZD6474, an acceptable strategy for symptomatic management is initiation of loperamide 2mg po administered following the first episode, which can be repeated as frequently as every 2 hours while awake (or administered at a dose of 4mg every 4 hours during sleeping hours) (not to exceed a total of 16mg/24 hours) until the patient is diarrhea-free for 8-12 hours.

No dose modifications will be made for CTCAE grade 1 or 2 nausea, vomiting or diarrhea. If CTCAE grade 3 nausea, vomiting, or diarrhea develops despite optimal pharmacologic prophylaxis/treatment, study medication should be withheld until symptoms resolve to less than or equal to grade 1. Once the diarrhea resolves to less than or equal to grade 1, treatment with ZD6474 may recommence with a dose reduction of one level. If the toxicity reoccurs on the dose reduction pack, the subject will be withdrawn from the study. Subjects who develop grade 4 nausea, vomiting, or diarrhea will discontinue therapy with ZD6474. Subjects who are clinically unstable because of nausea, vomiting, diarrhea or other intercurrent medical illness must be admitted and evaluated using telemetry until clinically stable.

3.3.3 QT prolongation

QT prolongation will be managed as follows:

Monitoring for QT prolongation

All patients on study will get a weekly 12 lead EKG for the first 2 cycles. Thereafter (in the absence of QT prolongation), a monthly ECG will be performed while the patient is on the study drug. The following algorithm will be used to monitor/manage QTc prolongation.

QTc prolongation is defined as

A single QTc value of ≥ 500 msec or an increase of ≥ 100 msec from baseline;

[figure not shown]
OR

Two QTc measurements where either of the following criteria are met for both QTc values (the second being the mean of 3 consecutive ECGs):

A QTc interval ≥ 500 msec but < 550 msec, **OR**
An increase of ≥ 60 msec, but < 100 msec, from baseline QTc to a QTc value ≥ 480 msec.
Management of Patients With QTc Prolongation

For a single QTc value of ≥ 500 msec or an increase of ≥ 100 msec from baseline, ZD6474 must be withheld. ECGs and electrolytes should be followed 3 times a week until QTc falls below 480 msec or baseline, whichever is higher. ZD6474 treatment may be resumed at a lower dose after the QTc recovers to < 480 msec or baseline.

For a QTc ≥ 500 ms but < 550 ms (grade 3 CTCAE v3.0) or ≥ 60 ms, but < 100 ms compared to baseline to a QTc value ≥ 480 msec, further ZD6474 dosing will be withheld and an ECG (in triplicate) obtained within 24 hours. If the repeat ECGs confirm a QTc ≥ 500 (mean calculated from 3 ECGs) or prolongation of ≥ 60 ms from baseline to a QTc ≥ 480 ms, QTc and electrolytes will be monitored three times a week until the QTc returns to baseline or below 480ms (whichever is higher); thereafter, ZD 6474 will be resumed at one lower dose level. If the repeat ECG reveals a QTc < 500 ms or a prolongation of < 60 ms from baseline, ZD6474 will be resumed at the current dose and an ECG repeated in 48 hours and thereafter as outlined in the study plan in the absence of QT prolongation (i.e., ≥ 500 ms or prolongation ≥ 60 ms from baseline to a value ≥ 480 msec). A second instance of QTc ≥ 500 ms (but < 550 ms) or QTc prolongation ≥ 60 ms from baseline to a value ≥ 480 msec will necessitate withholding drug until normalization of QTc and resumption thereafter at one lower dose level.

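### Section 3.3.3 gives conflicting restart instructions after QTc prolongation, both for an unconfirmed index QTc of 500–549 ms and for repeat means that fall in both branches of the confirmation rule

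*Combined protocol and SAP*

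**What the plan says.** Section 3.3.3 first defines QTc prolongation. One value of at least 500 ms, or one rise of at least 100 ms, is enough. Alternatively, two measurements (the second a mean of three ECGs) must both lie at 500–549 ms, or both show a rise of 60–99 ms to at least 480 ms. A figure sits inside this definition and is not in the text available for review.

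Two management paragraphs follow.

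- **Single-value rule.** "For a single QTc value of ≥ 500 msec or an increase of ≥ 100 msec from baseline, ZD6474 must be withheld". ECGs and electrolytes are followed three times a week until QTc is below the higher of 480 ms and baseline. Then: "ZD6474 treatment may be resumed at a lower dose after the QTc recovers to < 480 msec or baseline".
- **Confirm rule.** It opens "For a QTc ≥ 500 ms but < 550 ms (grade 3 CTCAE v3.0" and also covers a rise of 60–99 ms to at least 480 ms. In these cases "further ZD6474 dosing will be withheld and an ECG (in triplicate) obtained within 24 hours".
  - *Confirmed branch:* "If the repeat ECGs confirm a QTc ≥ 500 (mean calculated from 3 ECGs) or prolongation of ≥ 60 ms from baseline", to a value of at least 480 ms. The drug stays on hold until recovery and resumes one level lower.
  - *Unconfirmed branch:* "If the repeat ECG reveals a QTc < 500 ms or a prolongation of < 60 ms from baseline". Then "ZD6474 will be resumed at the current dose and an ECG repeated in 48 hours", with the usual ECG schedule afterwards "in the absence of QT prolongation (i.e., ≥ 500 ms or prolongation ≥ 60 ms from baseline to a value ≥ 480 msec".

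A last sentence says that a further episode in the confirm rule's range leads to a hold until QTc normalises and restart one level lower.

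**The concern.** The section fails to give a single instruction in two situations.

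1. **The two rules overlap.** The single-value rule has no upper limit at 550 ms and no exception for a repeat ECG that fails to confirm. A patient at 500–549 ms is therefore under both rules, and the written text gives no precedence.
2. **The two branches of the confirm rule overlap.** The unconfirmed condition is not the negation of the confirmed one. Some repeat means satisfy both and receive two different restart instructions.

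What is at stake is patient safety and consistent dosing. Section 1.2.5 lists torsade-de-pointes among events possibly related to the drug. Read literally, the second overlap allows the full current dose to restart about a day after the index ECG while prolongation is still confirmed. The opposite error also has a cost: an unneeded step from 300 to 200 mg (Section 3.3) removes one third of the dose.

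**Working it through.** **Inputs.** The thresholds are those of Section 3.3.3. Baseline is assumed to be the screening QTc, which Section 2.1.2 requires to be below 480 ms; recovery then means below 480 ms. Values are whole milliseconds. B is baseline, I the index QTc and R the repeat mean.

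- Single-value rule applies: I ≥ 500, or I − B ≥ 100.
- Confirm rule applies: 500 ≤ I < 550, or (60 ≤ I − B < 100 and I ≥ 480).
- Confirmed: R ≥ 500, or (R − B ≥ 60 and R ≥ 480).
- Unconfirmed: R < 500, or R − B < 60.

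**Step 1: both rules met.** Any I from 500 to 549 meets both rules at every baseline. What follows depends on R:

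| Baseline | R < 480 | R 480–499 | R ≥ 500 |
|---|---|---|---|
| 420 | dose conflict | both branches (step 2) | rules agree |
| 440 | dose conflict | dose and timing conflict | rules agree |
| 460 | dose conflict | dose and timing conflict | 500–519 both branches; 520 or more, rules agree |

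Two examples with B = 440 and I = 510:

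- R = 470: the single-value rule gives a lower dose; the confirm rule gives the current dose.
- R = 490 (rise 50): the single-value rule keeps the drug on hold until QTc is below 480; the confirm rule restarts the current dose now.

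**Step 2: both branches met.** Confirmed and unconfirmed hold together in two regions.

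- 480 ≤ R ≤ 499 with R − B ≥ 60. This needs B + 60 ≤ 499, so B ≤ 439.
- R ≥ 500 with R − B < 60. This needs 500 ≤ B + 59, so B ≥ 441.

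| Baseline | Repeat means in both branches |
|---|---|
| up to 420 | 480–499 (20 values) |
| 430 | 490–499 |
| 439 | 499 |
| 440 | none |
| 441 | 500 |
| 450 | 500–509 |
| 460 | 500–519 |
| 479 | 500–538 |

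No repeat mean falls outside both branches as written, because failing the confirmed test implies R < 500.

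The second problem does not depend on the first. With B = 420, I = 490 and R = 490, the rise is 70 ms, so the single-value rule does not apply. The patient meets the two-measurement definition of prolongation, yet goes both to one lower level after recovery and to the current dose now.

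**Step 3: exposure after a literal restart.** Section 1.2.5 gives a terminal half-life of about 4–5 days. Assume steady state on 300 mg/day and a single-exponential, continuous-input approximation. Levels are fractions of the pre-hold level; the first figure in each pair is for a 4-day half-life, the second for 5 days.

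- After a 1-day hold: 2^(−1/4) = 0.84; 2^(−1/5) = 0.87.
- 48 hours after restarting 300 mg: 1 − (1 − 0.841) × 2^(−2/4) = 0.89; 1 − (1 − 0.871) × 2^(−2/5) = 0.90.
- Still on hold at that time (3 days): 2^(−3/4) = 0.59; 2^(−3/5) = 0.66.

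At the 48-hour ECG the level is thus 89–90% of the pre-hold level after a literal restart, against 59–66% if the hold had continued.

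**The case against.** The strongest reply is that the second overlap is a drafting slip with visible intent. The confirmed branch comes first, and both the definition and the parenthesis closing the unconfirmed sentence treat a rise of at least 60 ms to at least 480 ms as prolongation. A careful clinician would stop at the confirmed branch. This is right about intent, but the operative sentence still orders the current dose.

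For the first overlap, the omitted figure may show an order of steps, so the lack of precedence can be asserted only for the written text. The confirm rule is also the more specific one, and the sentence on a further episode adds nothing at 500–549 ms unless that rule governs. Against this, the definition already counts a single value of 500 ms or more as prolongation. The text points both ways. The figure cannot alter the or in the unconfirmed branch.

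Safeguards also exist. Both rules hold the drug at once. An ECG follows 48 hours after restart, a further episode forces a reduction, ECGs are weekly in the first two cycles, and Section 3.9 lets the investigator stop unsafe treatment. These shorten a wrong restart but do not say which instruction to follow.

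The exposure figures cannot be turned into milliseconds. Section 1.2.5 gives a slope of 0.0243 ms per ng/ml, but the available text gives no steady-state concentration. That limit stands.

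**Conclusion.** The concern holds and should be fixed. An index QTc of 500–549 ms always meets both rules. They disagree on restart dose whenever the repeat does not confirm, and also on timing when that repeat is 480–499 ms. They agree when the repeat mean is at least 500 ms with a rise of at least 60 ms. The branches of the confirm rule overlap at every whole-millisecond baseline below 480 ms except 440. The overlap spans up to 20 values for baselines up to 439 ms and up to 39 values (500–538 ms) at a baseline of 479.

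These are ranges of QTc, not shares of patients. The documents do not show how often QTc reaches 500 ms; one trial at 300 mg reported prolongation in 20.5%, all grade 1 (Section 1.2.5). The ranges assume that baseline is the screening value. The protocol also takes a pre-dose ECG on day 1, for which no cap is stated. The two-stage response design is not affected.

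**What to change.** 1. **Make the unconfirmed branch the exact complement of the confirmed one:** repeat mean QTc below 500 ms, and not a rise of at least 60 ms to a value of at least 480 ms. Over baselines 350–479 and repeats 350–699 ms this leaves no gap and no overlap. Merely replacing the or with an and is not enough. For baselines of 419 ms or less it leaves repeats from B + 60 to 479 in neither branch (460–479 at a baseline of 400).
2. **Add one sentence saying which rule governs when an index ECG meets both triggers.** The clinical team should choose, after checking the figure; the single-value rule is the more cautious. Raising the single-value threshold to 550 ms would not do this alone. Both triggers would still be met by rises of at least 100 ms to 500–549 ms (baselines up to 449) and by rises of 60–99 ms to at least 550 ms (baselines 451–479).
3. **Align the definition and the sentence on a further episode** with the rule chosen.

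The cost is a protocol amendment to the wording, with no new assessments.

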Several phase I trials have been conducted in human subjects. Trial 6474IL/0001 (Western study) was conducted as a multicenter, dose escalation phase I trial evaluating 50, 100, 200, 300, 500 and 600mg doses administered orally as a daily single dose. A total of 77 patients have been treated on this trial at various dose levels, including an expanded cohort of 19 and 25 patients respectively at the 100mg and 300mg dose levels who were enrolled to better evaluate the effect of ZD6474 on QT interval and ST, T wave changes. A second phase I trial conducted in Japan (TVE-15-11) followed a dose escalation pattern evaluating 100, 200, 300 and 400mg daily oral doses. A total of 18 patients have been accrued on this trial.

Pharmacokinetics

Pharmacokinetic data obtained from the Western and Japanese studies were comparable. Absorption was highly variable, with individual patients having a T_{max} as late as 24 hours post-dose. Following achievement of maximum plasma concentration, C_{max} declined in a biphasic manner. Terminal half-life was estimated to be about 4-5 days and appeared to be independent of dose. Both mean AUC and C_{max} increased with increasing dose in a linear manner with about 2 to 6 fold in inter-individual variability in AUC for a given dose. A comparison of the mean weekly trough levels suggest that steady state was achieved by day 29, with marked accumulation between day 1 and 29.

Adverse Events

The most common adverse events seen on both trials were:

- 1) Rash- At least 2 distinct types of rash were seen- A macular erythema and a follicular (acneiform) rash. Rash was reported in 54 (72%) patients in the Western and 14 (77.8%) patients in the Japanese study. The occurrence of rash appeared to be dose-dependent.

- 2) Gastrointestinal toxicity- Diarrhea was reported in 42 (56%) of the Western patients and 10 (56%) of the Japanese patients. Other common GI side effects seen the western and Japanese studies included nausea (39% in the Western and 22% in the Japanese studies), vomiting (22% and 17% respectively), anorexia (29% and 28% respectively) and constipation (24% in the Western study).
- 3) Central Nervous System- Headaches were reported by 19 (25%) patients and dizziness by 14 (17%) patients in the Western study. 27% of the patients in the Japanese study reported headaches.
- 4) Cardiovascular toxicity-
 - a. In the western trial, 6 patients (8%) had T-wave or ST-segment changes consistent with repolarization abnormalities.

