- QTc with Bazett's correction that is unmeasurable, or ≥ 480 msec on screening ECG. If a patient has QTc ≥ 480 msec on screening ECG, the screen ECG may be repeated twice (at least 24 hours apart). The average QTc from the three screening ECGs must be < 480 msec in order for the patient to be eligible for the study). Patients who are receiving a drug that has a risk of QTc prolongation (see [Appendix C](#), Group/Table 2) are excluded if QTc is ≥ 460 msec.
- Potassium concentration less than 4.0 mEq/L, calcium (ionized calcium or adjusted for albumin), or magnesium concentrations outside normal limits despite optimal supplementation/correction
- Left ventricular ejection fraction less than 45% measured by multiple gated acquisition scan (MUGA) or echocardiogram (ECHO)
- Hypertension not controlled by medical therapy (systolic blood pressure greater than 150 mmHg or diastolic blood pressure greater than 100 mmHg).
- Uncontrolled intercurrent illness including, but not limited to, ongoing or active infection, symptomatic congestive heart failure, unstable angina pectoris, cardiac arrhythmia, or psychiatric illness/social situations that would limit compliance with study requirements.
- Patient known to be HIV positive and requiring antiretroviral therapy
- Currently active diarrhea that may affect the ability of the patient to absorb ZD6474 or tolerate further diarrhea.
- Patients on therapeutic anticoagulation
- Patients with known bleeding disorders
- Pregnant women are excluded from this study because ZD6474 is an anti-angiogenic agent with the potential for teratogenic or abortifacient effects. Because there is an unknown but potential risk for adverse events in nursing infants secondary to treatment of the mother with ZD6474, breastfeeding should be discontinued if the mother is treated with ZD6474
- Any known hypersensitivity to ZD 6474 or other excipients of ZD6474

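### In 3.3.3, for baseline QTc below 380 ms, the 480 ms release limit can end intensive monitoring and permit restart while the ≥100 ms hold criterion is still met

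*Combined protocol and SAP*

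**What the plan says.** Section 3.3.3 (QT prolongation) sets a mandatory hold on a single ECG with QTc of 500 ms or more, or on a large rise: "an increase of ≥ 100 msec from baseline, ZD6474 must be withheld". The rise condition carries no minimum QTc. The same section counts a single rise of that size as QTc prolongation by definition.

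Two sentences govern release from this hold:

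- Monitoring: "ECGs and electrolytes should be followed 3 times a week until QTc falls below 480 msec or baseline, whichever is higher".
- Restart: "ZD6474 treatment may be resumed at a lower dose after the QTc recovers to < 480 msec or baseline".

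Section 2.1.2 limits screening QTc from above only. If the first ECG reads 480 ms or more, "The average QTc from the three screening ECGs must be < 480 msec". No lower limit is set, so a baseline below 380 ms is eligible.

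Routine ECGs are weekly for the first two cycles. They then become monthly, provided there is no QT prolongation.

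**The concern.** A hold rule and its release rule should fit together: meeting the release limit should mean that the reason for the hold has gone. Here the trigger is measured against the patient's own baseline and the release against a fixed 480 ms. For a patient with a low baseline, QTc can be under 480 ms and still be 100 ms or more above baseline.

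Two situations follow. In the first, QTc rises past 480 ms, then falls back below it without the rise having dropped under 100 ms. The monitoring end point and the restart limit are then met while the hold criterion still applies. In the second, the triggering ECG is itself below 480 ms, so the section offers no numeric recovery target.

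What is at stake is patient safety in a small subset. Section 1.2.5 lists torsade de pointes and ventricular tachycardia among the reported events, and the drug accumulates markedly up to day 29. After cycle 2 the gap is wider. Once thrice-weekly ECGs end, the monthly schedule applies only without QT prolongation, which such a patient still has by the section's own definition. No other schedule is given for that state.

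**Working it through.** The plan states no figure to reproduce on this point. The check is on threshold logic, followed by an estimate of what the fix costs.

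**Inputs.** From 3.3.3: rise trigger 100 ms; release limit 480 ms, or baseline if higher. From 2.1.2: screening QTc below 480 ms, taken here as the baseline. From 1.2.5: "Terminal half-life was estimated to be about 4-5 days and appeared to be independent of dose", and a linear QTc effect of 0.0243 ms per ng/ml.

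**Step 1: where trigger and release overlap.** Let B be baseline and Q the current QTc, in ms.

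- Rise trigger met: Q − B ≥ 100.
- Monitoring ends: Q < max(480, B). Since B < 480, this is Q < 480.
- Restart permitted: Q < 480 is enough, because the sentence says 480 ms *or* baseline.

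All three hold when B + 100 ≤ Q < 480, which needs B < 380. In whole milliseconds the band is 380 − B values wide.

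| Baseline | QTc values meeting both trigger and release |
|---|---|
| 350 | 450–479 |
| 365 | 465–479 |
| 379 | 479 only |
| 380 or more | none |

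Enumerating every whole-ms pair with B from 300 to 479 gives 3,240 overlapping pairs (the sum 1 + 2 + … + 80, from B = 379 down to 300). None has B of 380 or more.

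**Step 2: the two situations.**

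- Recovery: B = 350, trigger 510 (+160), follow-up 470. QTc has fallen below 480, but 470 − 350 = 120, so the hold criterion is still met.
- Trigger inside the band: B = 365, Q = 470, rise 105. The reading that starts the hold is already under 480. A later 469 ms would be lower and under 480, yet still +104.

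**Step 3: effect of the added condition.** Requiring Q − B < 100 as well makes the release limit min(480, B + 100): 450 for B = 350, 465 for B = 365, and 480 for every B from 380 to 479. No overlapping pair remains.

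**Step 4: extra hold time.** Assume that the whole rise is drug effect, that it is proportional to concentration, and that concentration halves every 4-5 days. Going from rise r₁ to rise r₂ takes log₂(r₁/r₂) half-lives.

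- Trigger at or above 480, extra wait beyond the 480 limit, log₂((480 − B)/100):
  - B = 365: log₂(1.15) = 0.202, or 0.8-1.0 days.
  - B = 350: log₂(1.30) = 0.379, or 1.5-1.9 days.
  - B = 340: log₂(1.40) = 0.485, or 1.9-2.4 days.
  - B = 380: log₂(1.00) = 0.
- Trigger inside the band, time for the rise to fall to 100, log₂(rise/100):
  - 365 to 470: log₂(1.05) = 0.070, or 0.28-0.35 days.
  - 350 to 479: log₂(1.29) = 0.367, or 1.5-1.8 days.

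The phase I concentrations "declined in a biphasic manner", so the early fall may be faster than these times suggest.

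**Step 5: how likely.** On the reported slope, a 100 ms effect needs 100/0.0243 ≈ 4,115 ng/ml. The documents give neither a baseline QTc distribution nor a rate of rises of 100 ms or more, so no count of affected patients can be derived.

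**The case against.** The strongest reply is about wording. The hold is compulsory, whereas restart is optional, comes after recovery and is at a lower dose. Monitoring ends only when QTc has come down. An ECG that has just triggered the hold has neither fallen nor recovered, so the natural reading is to hold, follow, and then consider a lower dose. This stands against one inference a reader might draw, namely that a single ECG both forbids and orders treatment. The documents do not support that: nothing in 3.3.3 orders restart. The reply does not dispose of the recovery case. There, 470 ms after 510 ms is a true fall below 480 ms, and the section gives no other numeric target. Reading the release as a return to baseline contradicts the choice of the higher of the two values. Letting the compulsory hold override the optional restart is sensible, but the text does not say so.

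A second reply is that an absolute release limit is a legitimate design choice, since at baseline 380 the protocol accepts restart at 479 ms (+99). That is fair, and the limit itself is not criticised. At 380 ms and above, release implies that the rise trigger has cleared. Below 380 ms it does not.

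A reader might also take the rule for rises of 60 to under 100 ms, with its 480 ms floor, as a safe model. It is not one. Its repeat-ECG step resumes the current dose if QTc is under 500 ms *or* the rise is under 60 ms. A repeat of 490 ms from baseline 420 (+70) therefore both confirms the prolongation and clears it.

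The practical effect is small, and this stands. In the randomized comparison with gefitinib, QTc prolongation on ZD6474 was asymptomatic and all grade 1. Section 8.4.1 has the team discuss each patient, and section 3.9 lets the investigator stop unsafe treatment.

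**Conclusion.** The point holds as a minor defect in a safety rule. For baseline QTc below 380 ms, section 3.3.3 can end thrice-weekly monitoring and permit restart at a lower dose while the rise that compels a hold is still present. If the triggering ECG is already under 480 ms, no numeric recovery target exists. The 380 ms boundary is exact (480 − 100).

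The case appears rare: it needs a low baseline, a rise of 100 ms or more, and a QTc under 480 ms, in at most 37 patients. Its frequency cannot be estimated from the documents. The primary endpoint and the two-stage decision are unaffected.

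The logic assumes that baseline is the screening value below 480 ms, and that the figure not shown among the definitions in 3.3.3 leaves the written thresholds unchanged. The management text that sets those thresholds is complete. The hold times rest on the further assumptions in the working.

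**What to change.** In both the monitoring sentence and the restart sentence of 3.3.3, require a repeat ECG showing QTc below 480 ms (or baseline, if higher) **and** a rise from baseline below 100 ms. At baseline 350 the drug could then restart below 450 ms, and at 365 below 465 ms. From 380 ms up nothing changes.

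Putting a 480 ms floor on the trigger would also remove the overlap, but by dropping the hold for patients such as 365 to 470 ms. The added clause keeps the hold.

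The cost is one clause in two sentences of an amendment, at least one repeat ECG for each affected patient, and about 1-2 extra hold days at baselines of 350-365 ms when the trigger was at or above 480 ms, on the half-life assumptions above. Lower baselines wait somewhat longer. For triggers inside the band at baselines of 350-379 ms, the rise should clear within the 2-3 day gap between thrice-weekly ECGs, so the next one would normally suffice. If the sponsor already intends the compulsory hold to govern restart, the clause adds no hold time and only records that intention.
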